#### 7.4.3. Prediction modelling for humoral and cellular immune response

Descriptive long-term analysis of other ZOSTER studies indicated that both cellular and humoral gE-specific immune responses were highest at Month 3 and then declined until they began to plateau by Month 12 [Chlibek, 2016].

A mixed effect model for repeated measurements will be used to model over time the log10-transformation concentration of gE ELISA and the frequency of CD4 T-cells producing at least 2 immunological activation markers following stimulation with gE.

The covariates will include the log-transformed pre-vaccination response and the time (or the log-transformed of the time if needed) elapsed (measured in months) following the last vaccination. **CCI**

The model will contain a random intercept effect and, if data allows, the random slope effect. Indeed, the model allows for random individual deviations from the overall mean response (random intercept) and, if necessary, according to Schwarz' Bayesian Information Criterion (SBIC) and Akaike's information Criterion (AIC) goodness-of-fit statistics, for a random individual deviation from the immunogenicity endpoints decay over time (random coefficient [slope]).

Since the focus here is on long-term persistence rather than antibody rise induced by vaccination, and because it has proved difficult to apply modelling to the first rapid decay phase, the model will use data starting from 1 month post dose 2. Sensitivity analysis will use data starting from 1 year post dose 2. The model will include assay results from a time point provided that these were part of the ATP cohort for that time point (adapted ATP). ***The model is also going to be used to predict the antibody up to 15 years post vaccinations.*** Given the nonlinear nature of antibody decay, three mixed-effects models will be explored to model over time the immunogenicity endpoint: two exponential models proposed by [Fraser, 2007] and the piecewise model proposed by [David, 2009]

The first model used by Fraser is the conventional power-law model that includes the rate of immunogenicity endpoint decay to estimate the persistence of antibody levels over time after vaccination

The second model is the extension of the first model called modified power-law model and takes into account both antibody persistence over time and immune memory which would be involved in a long-term antibody plateau.

A third model, the piece-wise model fits the data based on two or three different non-overlapping intervals corresponding to the observed decay of vaccine-induced antibodies.

Using the model selection criteria of AIC, results from the best model selected out of those 3 mentioned above will be summarized.

The selection of the break points will be made using Akaike's information criterion and will depend on the data. **CCI**  
[REDACTED]  
[REDACTED]

## **7.5. Safety and reactogenicity**

### **7.5.1. Counting rule**

The way the percentage of subjects will be derived will depend on the event analysed (see the following table for details). As a result, the denominator (N) will differ from one table to another.

Event	N used for deriving %	Terminology used in the tables for N
Concomitant medication	All vaccinated subjects	Number of subjects with at least one administered dose
Solicited general symptom	All vaccinated subjects with at least one solicited general symptom documented as either present or absent	For each dose and overall/subject: N= number of subjects with at least one documented dose For overall/dose: N= number of documented doses
Solicited local symptom	All vaccinated subjects with at least one solicited local symptom documented as either present or absent	For each dose and overall/subject: N= number of subjects with at least one documented dose For overall/dose: N= number of documented doses
Unsolicited symptom from day 0 to day 29	All vaccinated subjects	Number of subjects with at least one administered dose
SAE/ Related SAE	All vaccinated subjects	Number of subjects with at least one administered dose

Documented dose= symptom screen completed

### **7.5.2. Grading rule**

The maximum intensity of local injection site redness/swelling will be scored at GSK Biologicals using GSK Biologicals' standard grading scale based on the US Food and Drug Administration (FDA) guidelines for Toxicity Grading Scale for Healthy Adult and Adolescent Volunteers enrolled in Preventive Vaccine Clinical Trials" (see protocol).

- 0 : < 20 mm diameter
- 1 :  $\geq 20 \text{ mm to } \leq 50 \text{ mm diameter}$
- 2 :  $> 50 \text{ mm to } \leq 100 \text{ mm diameter}$
- 3 :  $> 100 \text{ mm diameter}$

The preferred route for recording temperature in this study is oral. When there is no other alternative, the temperature may be recorded by another route. If the temperature is taken by another route (axillary, rectal or tympanic), the route should be documented.

Temperature (measured by oral, axillary or tympanic route) will be scored at GSK Biologicals as follows:

0	:	< 37.5°C
1	:	≥37.5°C – ≤ 38.0°C
2	:	>38.0- ≤ 39.0°C
3	:	> 39.0°C

Note that Fever is defined as temperature  $\geq 37.5^{\circ}\text{C}$  /  $99.5^{\circ}\text{F}$  for oral, axillary or tympanic route, or  $\geq 38.0^{\circ}\text{C}$  /  $100.4^{\circ}\text{F}$  for rectal route.

### **7.5.3. Conversion of temperature to °C**

The following conversion rule is used for the conversion of temperature to °C

$$\text{Temperature in } ^{\circ}\text{Celsius} = ((\text{Temperature in } ^{\circ}\text{Fahrenheit} - 32) * 5)/9$$

The result is rounded to 1 decimal digit.

## **7.6. Handling missing data for Reactogenicity and safety**

All efforts will be made during the study database cleaning, through queries to the investigators, to keep the number of missing recordings as small as possible.

### **7.6.1. Solicited general symptoms**

For a given subject and the analysis of solicited symptoms within 7 days post-vaccination, missing or non-evaluable measurements will not be replaced. Therefore, the analysis of the solicited symptoms based on the Total Vaccinated Cohort will include only vaccinated subjects for doses with documented safety data (i.e., symptom screen completed). This means that the analysis of solicited general symptoms will include all subjects for whom the question (1) in [Figure 3](#) about the presence of any solicited general symptom has been answered by 'Yes' or 'No' (see the GENSOL\_YN item).

The next sections describe how each subject contributes to the analyses, depending on the endpoints.

Figure 3 Information captured in the clinical database for solicited general symptoms

SOLICITED ADVERSE EVENTS - GENERAL SIGNS/SYMPOMTS - TEMPERATURE	
2.* Has the subject experienced any of the General Solicited signs/symptoms between Day 0 and Day 6?	
[GENSOL_1_YN]   [A:Y]  [A:N] -> Please:   tick No/Yes for each sign/symptom and complete further as necessary in the "General solicited signs/symptoms (except temperature)" form.   complete the "Temperatures" form.   [A:N] [A:Y] -> Please complete the "Temperatures" form   [A:U] [A:U] -> Unknown, no information available


ZOSTER-049 EXT:006-022(201190): SOLICITED ADVERSE EVENTS - GENERAL SIGNS/SYMPOMTS (General signs/symptoms)
 
If any of these adverse events meets the definition of serious, complete an Expedited Adverse Event Report.
 
HEADACHE
 
1.* Occurred?
 
[HE_1_YN]   [A:N]  [A:Y]  [SYMP_VAL_INTEN]    Yes -> [SYMP_VAL_INTEN_D0] [SYMP_VAL_INTEN_D1] [SYMP_VAL_INTEN_D2] [SYMP_VAL_INTEN_D3] [SYMP_VAL_INTEN_D4] [SYMP_VAL_INTEN_D5] [SYMP_VAL_INTEN_D6]    Intensity Day 0: [INTENSITYSOL]  [INTENSITYSOL]     Day 1: [INTENSITYSOL]  [INTENSITYSOL]     Day 2: [INTENSITYSOL]  [INTENSITYSOL]     Day 3: [INTENSITYSOL]  [INTENSITYSOL]     Day 4: [INTENSITYSOL]  [INTENSITYSOL]     Day 5: [INTENSITYSOL]  [INTENSITYSOL]     Day 6: [INTENSITYSOL]  [INTENSITYSOL]     [HE_ONG]    After Day 6: Ongoing?  [A:N]  [A:Y]  [SYMP_ONG_INTEN]    Yes -> [SYMP_MAX_INTEN]    Maximum intensity: [INTENSITYSOLMAX]     [ERDAT]    Date of last day of sign/symptom: [Req/Unk]  / [Req/Unk]  / [Req]  (1900-2025)    [CONT-END]    Continuing at the end of the study?  [A:Y]     [CAUSAL]    Is there a reasonable possibility that the AE may have been caused by the investigational product?  [A:Y]  [A:N] Yes   [A:N]  [A:Y] No    [MED_TYPE]    Medically attended visit:  [A:ER] Emergency Room   [A:HO] Hospitalisation   [A:MD] Medical Personnel   [A:NO] None 
	

The following rules will be used in the analysis of each solicited general symptom:

- Subjects who documented the absence of a specific solicited symptom after one dose (i.e. if the answer to question (2) in [Figure 3](#) is "No" ex HE\_YN=N)) will be considered not having that symptom after that dose.
- Subjects who documented the presence of a specific solicited symptom after one dose (i.e. if the answer to question (2) in [Figure 3](#) is "Yes"(ex HE\_YN=Y)) without having recorded any daily measurement will not be counted in the summary of subjects with symptoms above a specified threshold, however they will be part of the summary corresponding to the 'All' category.).
- Subjects who documented the presence of a specific solicited symptom (i.e. if the answer to question (2) in [Figure 3](#) is "Yes" ex HE\_YN=Y)) and fully or partially recorded daily measurement over the solicited period will be included in the summaries at that dose and classified according to their maximum observed daily recording over the solicited period.
- Doses without symptom screen documented will be excluded.

For summary of temperature

To allow the temperature recording, a separate screen has had to be completed whatever the answer to question (2) in [Figure 4](#) and even if no temperature equal or above 37.5°C has been found in the diary card.

All subjects for whom that question (2) in [Figure 4](#) has been answered by "Yes" or "No", will be included in the summaries of temperature by **half degree (°C) cumulative increments** and classified according to their maximum temperature value observed daily recording over the solicited period. If no daily measurement is recorded for temperature, the subject will not be counted in the summary of subjects with temperature above a specific threshold. For the summary of temperature, the "all" category will not be computed. This table will be produced overall, and by route with no route conversion

## CONFIDENTIAL

201190 (ZOSTER-049 EXT:006-022)  
Statistical Analysis Plan Amendment 3

Figure 4 Information captured in the clinical database for temperature record

ZOSTER-049 EXT:006-022(201190): TEMPERATURES (Temperatures)																																																													
TEMPERATURES																																																													
1.	
Temperature (Celsius/Fahrenheit) collected daily from Day 0 to Day 6
 
 
 Day 0: 	Day 1: 	Day 2: 	Day 3: 	Day 4: 	Day 5: 	Day 6: 	
 
 [FE_VAL]	[FE_VAL]	[FE_VAL]	[FE_VAL]	[FE_VAL]	[FE_VAL]	[FE_VAL]	
 
 [FE_NT]	[FE_NT]	[FE_NT]	[FE_NT]	[FE_NT]	[FE_NT]	[FE_NT]	
 
 Not taken	
 
 [A:Y] 	
 
									Day 0: 	Day 1: 	Day 2: 	Day 3: 	Day 4: 	Day 5: 	Day 6: 	[FE_VAL]	[FE_VAL]	[FE_VAL]	[FE_VAL]	[FE_VAL]	[FE_VAL]	[FE_VAL]	[FE_NT]	[FE_NT]	[FE_NT]	[FE_NT]	[FE_NT]	[FE_NT]	[FE_NT]	Not taken	Not taken	Not taken	Not taken	Not taken	Not taken	Not taken	[A:Y] 	[A:Y] 	[A:Y] 	[A:Y] 	[A:Y] 	[A:Y] 	[A:Y] 																	
Day 0: 	Day 1: 	Day 2: 	Day 3: 	Day 4: 	Day 5: 	Day 6: 																																																							
[FE_VAL]	[FE_VAL]	[FE_VAL]	[FE_VAL]	[FE_VAL]	[FE_VAL]	[FE_VAL]																																																							
[FE_NT]	[FE_NT]	[FE_NT]	[FE_NT]	[FE_NT]	[FE_NT]	[FE_NT]																																																							
Not taken	Not taken	Not taken	Not taken	Not taken	Not taken	Not taken																																																							
[A:Y] 	[A:Y] 	[A:Y] 	[A:Y] 	[A:Y] 	[A:Y] 	[A:Y] 																																																							
2.	
Unit: 
 
[TEMP_UNIT] (A:CE)  Celsius (A:FA)  Fahrenheit
																																																												
3.	
Primary route: The preferred route for recording temperature in this study is oral. When there is no other alternative, the temperature may be recorded by other route. If the temperature is taken by another route (axillary, rectal or tympanic), the route should be documented. [Primary route]
 
[TEMP_ROUTE] (A:O)  Oral (A:A)  Axillary (A:R)  Rectal (A:T)  Tympanic
																																																												
4.*	
Did a temperature above or equal to threshold occur? i.e. during the solicited period at least one axillary/oral/tympanic measure is above or equal to 37.5° C/99.5° F or at least one rectal measure is above or equal to 38.0°C/100.4° F
 
 
 [FE_YN]	[A:N]  No	[A:NT]  Not taken	[A:Y]  [FE_ONG]	
 
 Yes -> After Day 6: Temperature above or equal to threshold? [A:N]  No	
 
 [A:Y]  [SYMP_ONG_TEMP]	
 
 [SYMP_MAX_TEMP]	
 
 Yes -> Max temperature (Celsius/Fahrenheit): 	
 
 [ERDAT]	
 
 End date:  /  /  (1900-2025)	
 
 [CONT_END]	
 
 Continuing at the end of the study? [A:Y] 	
 
 [CAUSAL]	
 
 Is there a reasonable possibility that the AE may have been caused by the investigational product? [A:Y]  Yes	
 
 [A:N]  No	
 
 [MED_TYPE]	
 
 Medically attended visit: [A:ER]  Emergency Room	
 
 [A:HO]  Hospitalisation	
 
 [A:MD]  Medical Personnel	
 
 [A:NO]  None	
 
									[FE_YN]	[A:N]  No	[A:NT]  Not taken	[A:Y]  [FE_ONG]	Yes -> After Day 6: Temperature above or equal to threshold? [A:N]  No			[A:Y]  [SYMP_ONG_TEMP]			[SYMP_MAX_TEMP]			Yes -> Max temperature (Celsius/Fahrenheit): 			[ERDAT]			End date:  /  /  (1900-2025)			[CONT_END]			Continuing at the end of the study? [A:Y] 			[CAUSAL]			Is there a reasonable possibility that the AE may have been caused by the investigational product? [A:Y]  Yes			[A:N]  No			[MED_TYPE]			Medically attended visit: [A:ER]  Emergency Room			[A:HO]  Hospitalisation			[A:MD]  Medical Personnel			[A:NO]  None		
[FE_YN]	[A:N]  No	[A:NT]  Not taken	[A:Y]  [FE_ONG]																																																										
Yes -> After Day 6: Temperature above or equal to threshold? [A:N]  No																																																													
[A:Y]  [SYMP_ONG_TEMP]																																																													
[SYMP_MAX_TEMP]																																																													
Yes -> Max temperature (Celsius/Fahrenheit): 																																																													
[ERDAT]																																																													
End date:  /  /  (1900-2025)																																																													
[CONT_END]																																																													
Continuing at the end of the study? [A:Y] 																																																													
[CAUSAL]																																																													
Is there a reasonable possibility that the AE may have been caused by the investigational product? [A:Y]  Yes																																																													
[A:N]  No																																																													
[MED_TYPE]																																																													
Medically attended visit: [A:ER]  Emergency Room																																																													
[A:HO]  Hospitalisation																																																													
[A:MD]  Medical Personnel																																																													
[A:NO]  None																																																													

## 7.6.2. Solicited local symptoms

The analysis of solicited local symptoms will include all subjects for whom the question (1) in [Figure 4](#) about the presence of a solicited local symptoms has been answered by 'Yes' or 'No' (see LOCSOL\_YN item).

The next sections describe how each subject contributes to the analyses, depending on the endpoints.

**Figure 5 Information captured in the clinical database for solicited local symptoms**

ZOSTER-049 EXT:006-022(201190): SOLICITED SYMPTOMS (Solicited symptoms)	
SOLICITED ADVERSE EVENTS - LOCAL SIGNS/SYMPOMTS	
1.* Has the subject experienced any of the Local Solicited signs/symptoms between Day 0 and Day 6?	 [LOCSOL_YN] [A:Y]  Yes -> Please tick No/Yes for each sign/symptom and complete further as necessary [A:N]  No [A:U]  Unknown, no information available
1	

ZOSTER-049 EXT:006-022(201190): SOLICITED ADVERSE EVENTS - LOCAL SIGNS/SYMPOMTS (HZ/su VACCINES) (Local signs/symptoms)	
If any of these adverse events meets the definition of serious, complete an Expedited Adverse Event Report.	
REDNESS	
1.* Occurred?	 [RE_YN] [A:N]  No [A:Y]  [SYMP_VAL_MM] Yes -> [SYMP_VAL_MM_D0] [SYMP_VAL_MM_D1] [SYMP_VAL_MM_D2] [SYMP_VAL_MM_D3] [SYMP_VAL_MM_D4] [SYMP_VAL_MM_D5] [SYMP_VAL_MM_D6] Size (mm): Day 0:  Day 1:  Day 2:  Day 3:  Day 4:  Day 5:  Day 6:    [RE_ONG] After Day 6: Ongoing? [A:N]  No [A:Y]  [SYMP_ONG_MM] Yes -> [SYMP_MAX_SIZE] Maximum size:    [ENDAT] Date of last day of sign/symptom:  / Reg/Link  / Reg  (1900-2025)   [CONT_END] Continuing at the end of the study? [A:Y] 
2	
 [MED_TYPE] Medically attended visit: [A:ER]  Emergency Room [A:HO]  Hospitalisation [A:MO]  Medical Personnel [A:NO]  None	

The following rules will be used in the analysis of each solicited local symptom:

- Subjects who documented the absence of a specific solicited symptom after one dose (i.e. if the answer to question (2) in [Figure 5](#) is "No" (ex RE\_YN=N)) will be considered not having that symptom at the injection site after that dose.
- Subjects who documented the presence of a specific solicited symptom after one dose (i.e. if the answer to question (2) in [Figure 5](#) is "Yes" (ex RE\_YN=Y)) without having recorded any daily measurement will not be counted in the summary of subjects with symptoms above a specified threshold, however they will be part of the summary corresponding to the 'All' category.).
- Subjects who documented the presence of a specific solicited symptom (i.e. if the answer to question (2) in [Figure 5](#) is "Yes" (ex RE\_YN=Y)) and fully or partially recorded daily measurement over the solicited period (e.g., intensity missing for Day 3) will be included in the summaries at that dose and classified according to their maximum observed daily recording over the solicited period.
- Doses without symptom screen documented will be excluded.

### 7.6.3. Combined Solicited local and general symptoms

The analysis of the combined solicited general and local symptoms will include all vaccinated subjects for whom the question (1) in [Figure 3](#) or [Figure 5](#) about the presence of any solicited general or local symptoms has been answered by 'Yes' or 'No'.

### 7.6.4. Unsolicited symptoms

All vaccinated subjects will be considered for the analysis of unsolicited symptoms.

The analysis of unsolicited adverse events, including serious adverse events, consists of evaluating the percentage of subjects with at least 1 report of an unsolicited adverse event classified by the Medical Dictionary for Regulatory Activities (MedDRA).

Subjects who missed reporting unsolicited symptoms will be treated as subjects without unsolicited symptoms.

### 7.6.5. Combined unsolicited symptoms with Solicited local and general symptoms

The analysis of the combined unsolicited symptoms with solicited general and local symptoms will include all vaccinated subjects.

- For analysis as per MedDRA classification that combines solicited and unsolicited symptoms, the following lower-level term will be used for the solicited symptoms:

Solicited Symptom Code	Value	Source Verbatim Text	LLT Name	LLT Code	PT Name	PT Code
FA	FA	FATIGUE	Fatigue	10016256	Fatigue	10016256
GI	GI	GASTROINTESTINAL	Gastrointestinal disorder	10017944	Gastrointestinal disorder	10017944
HE	HE	HEADACHE	Headache	10019211	Headache	10019211
MY	MY	MYALGIA	Myalgia	10028411	Myalgia	10028411
PA	PA	PAIN	Pain	10033371	Pain	10033371
RE	RE	REDNESS	Erythema	10015150	Erythema	10015150
SH	SH	SHIVERING	Shivering	10040558	Chills	10008531
SW	SW	SWELLING	Swelling	10042674	Swelling	10042674
TE	TE	TEMPERATURE/ fever	Fever	10016558	Pyrexia	10037660

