For the analysis of solicited symptoms, missing or non-evaluable measurements will not be replaced. Therefore, the analysis of the solicited symptoms based on the TVc will include only subjects/doses with documented safety data (i.e., symptom screen/sheet completed).

For the analysis of unsolicited symptoms/SAEs/pIMDs/concomitant medication, all vaccinated subjects will be considered and subjects who did not report an event will be considered as subjects without an event.

For the analysis of immunogenicity, missing or non-evaluable measurements will not be replaced. Therefore, a subject will be excluded from an analysis if all measurements are missing or non-evaluable.

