### **5. STUDY POPULATION**

#### **5.1. Total Vaccinated cohort**

The Total Vaccinated cohort (TVC) will include all subjects from the ZOSTER-006/022 studies who are enrolled in the ZOSTER-049.

The TVC for efficacy will include all subjects in the LTFU and control groups for whom data related to efficacy endpoints are available.

The TVC for the groups 1-Additional Dose and Revaccination will include all vaccinated subjects from the ZOSTER-006/022 studies who received at least one additional dose of HZ/su vaccine in the ZOSTER-049 study.

The TVC for the Control group will include vaccinated subjects from the ZOSTER-006/022 studies who are enrolled and randomized in Control group of ZOSTER-049.

The TVC for immunogenicity and humoral/CMI persistence will include subjects for whom data related to immunogenicity and humoral/CMI persistence endpoints are available.

The TVC for analysis of safety will include:

- For 1-Additional Dose and Revaccination groups only, the TVC for the analysis of solicited symptoms will include all subjects who received at least 1 dose of the study treatment in ZOSTER-049 and who have documented solicited symptoms (i.e., diary card for solicited AEs completed and returned).
- For 1-Additional Dose and Revaccination groups, the TVC for the analysis of any other AEs other than solicited symptom will include all subjects who received at least 1 dose of the study treatment in ZOSTER-049.
- For Control and LTFU groups, the TVC for the analysis of any AEs will include all subjects who came for Month 0 visit.

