#### 6.4.2. Additional considerations

Following analyses will be performed:

- *As part of safety endpoint assessment:*
  - *The percentage of subjects with at least one local (solicited and unsolicited) AE, with at least one general (solicited and unsolicited) AE and with any (solicited and unsolicited) AEs during the solicited 7-day follow-up period will be tabulated with exact 95% CI after each vaccine dose and overall (1-Additional Dose and Revaccination groups). The same tabulation will be performed for grade 3 solicited adverse events;*
- *Duration of each separate solicited local and general AE during the solicited follow-up period will be presented. Total duration of each individual (any and grade 3) solicited local and general AE will be tabulated. Tabulations will be provided on duration of solicited symptoms ongoing beyond the 7-day (Days 0-6) post vaccination period*
- *Number and percentage of subjects with fatal SAEs, classified by MedDRA Primary System Organ Class and Preferred Term will be presented with exact 95% CI in two ways:-*
  - *With respect to onset of fatal SAE:- With onset of fatal SAE within 30 days post each vaccination for 1-Additional Dose and Revaccination group and within 30 days post Month 0 and Month 2 visit for Control group; with onset of fatal SAE within 12 months post last vaccination for 1-Additional Dose and Revaccination group and within 12 months post Month 0 visit for Control group; with onset of fatal SAE from study start up to study end for all groups collected in Expedited AE report as per protocol.*
  - *With respect to date of death:- Who died within 30 days post each vaccination for 1-Additional Dose and Revaccination group and within 30 days post Month 0 and Month 2 visit for Control group; with death within 12 months post last vaccination for 1-Additional Dose and Revaccination group and within 12 months post Month 0 visit for Control group; with death from study start to study end for all groups collected in Expedited AE report as per protocol.*

*Please note – before protocol amendment 2, the fatal SAEs were collected in the Expedited AE report and after protocol amendment 2 only the related fatal SAE were reported in Expedited AE report.*

- *Listing of subjects who died (related and not related to vaccination before Protocol Amendment 2) and their fatal SAEs collected in Expedited AE report.*

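### In the supplementary Days 0-6 combined AE table, SAP 7.6.5 keeps all vaccinated subjects in N, so a missing diary counts as no solicited reaction and the combined percentage can fall below the solicited-only one

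*SAP*

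**What the plan says.** SAP 6.4.2 (Additional considerations) plans this table over the 7-day solicited period: "The percentage of subjects with at least one local (solicited and unsolicited) AE, with at least one general (solicited and unsolicited) AE". A third row covers AEs of either kind. The table is given with exact 95% CIs after each dose and overall, for the two vaccinated groups. SAP 6.4.1 and Protocol 11.7.4 plan the solicited-only version for the same groups, window and CI method.

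The two tables have different denominators:

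- **Combined, solicited plus unsolicited (SAP 7.6.5):** "The analysis of the combined unsolicited symptoms with solicited general and local symptoms will include all vaccinated subjects". There is no condition on documentation.
- **Solicited only, local plus general (SAP 7.6.3):** inclusion requires an answer on the general or the local symptom screen: "The analysis of the combined solicited general and local symptoms will include all vaccinated subjects for whom the question (1) in" (the sentence goes on to name the two screens).

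The documented-only condition for solicited symptoms recurs throughout:

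- Protocol 11.6.1 (Handling of missing data): "the analysis of the solicited symptoms based on the TVc will include only subjects/doses with documented safety data".
- SAP 5.1 limits the TVC for solicited symptoms to dosed subjects "who have documented solicited symptoms (i.e., diary card for solicited AEs completed and returned").
- SAP 7.5.1 sets N for general symptoms as "All vaccinated subjects with at least one solicited general symptom documented as either present or absent", with a matching entry for local symptoms.
- SAP 7.6.1: "missing or non-evaluable measurements will not be replaced"; doses without a completed screen are left out.

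Unsolicited events follow the opposite convention in Protocol 11.6.1 and SAP 7.6.4: N is all vaccinated subjects, and no report means no event. The counting table in SAP 7.5.1 has no entry for the combined analysis, so 7.6.5 alone sets its denominator.

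**The concern.** Each convention suits how its data are collected. Solicited reactions are recorded on a 7-day card, and without the card nobody knows whether they occurred. SAP 7.6.5 carries the unsolicited convention over to a table that also contains solicited events. A subject without a completed screen adds one to N but cannot add a solicited event. The SAP does not say in words that such a subject is symptom-free; that follows from including the subject in N. In effect it fills in missing solicited data as absent, which Protocol 11.6.1 rules out for solicited symptoms.

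Two things are at stake. First, the combined percentage understates how many subjects had a reaction if any diaries are missing. Second, the combined and solicited-only tables will be read together, and a wider set of events can then show a lower percentage. In groups of about 60, a few missing cards are enough for this to be visible.

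**Working it through.** The plan states no figure for this point, so there is none to reproduce. The check is arithmetic on proportions.

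**Inputs**

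- V, vaccinated subjects per group: about 60 (Protocol 6.1.1.2.1).
- D, subjects with documented solicited data. The documents give no expected value; 60, 59, 57 and 54 are assumed.
- S, documented subjects with a solicited AE. Not given; about 85% of D is assumed, rounded, with 50% as a check.
- x, subjects who count only through an unsolicited AE. Assumed 0 at first.

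**Formulas**

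- Solicited-only percentage = S/D (SAP 7.6.3, 7.5.1).
- Combined percentage = (S + x)/V (SAP 7.6.5).
- The combined figure is the lower one whenever x < S(V - D)/D.
- With x = 0, combined divided by solicited-only equals D/V, so the relative shortfall is the share of subjects without documentation.

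**Results for V = 60 and x = 0, with Clopper-Pearson 95% CIs**

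| Missing | S | Solicited-only | Combined | Drop (points) | x needed to match |
|---|---|---|---|---|---|
| 0 | 51 | 51/60 = 85.0% (73.4-92.9) | 51/60 = 85.0% (73.4-92.9) | 0 | 0 |
| 1 | 50 | 50/59 = 84.7% (73.0-92.8) | 50/60 = 83.3% (71.5-91.7) | 1.4 | 50 × 1/59 = 0.85 |
| 3 | 48 | 48/57 = 84.2% (72.1-92.5) | 48/60 = 80.0% (67.7-89.2) | 4.2 | 48 × 3/57 = 2.53 |
| 6 | 46 | 46/54 = 85.2% (72.9-93.4) | 46/60 = 76.7% (64.0-86.6) | 8.5 | 46 × 6/54 = 5.11 |

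At an assumed 50% event rate the drops are smaller:

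- 1 missing: 30/59 = 50.8% against 30/60 = 50.0%, 0.8 points.
- 3 missing: 28/57 = 49.1% against 28/60 = 46.7%, 2.5 points (from unrounded values).
- 6 missing: 27/54 = 50.0% against 27/60 = 45.0%, 5.0 points.

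**With some unsolicited-only subjects.** Take D = 54, S = 46 and x = 2, both documented. As written, solicited-only is 46/54 = 85.2% and combined is 48/60 = 80.0%. On the documented denominator for both, they are 46/54 = 85.2% and 48/54 = 88.9%. With a common denominator the combined figure cannot fall below the solicited-only one, because its numerator contains the other.

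**Why one documented N for all three rows is not enough.** The rule in 7.6.3 is met by a local or a general answer. A subject with only the local screen completed would stay in N for *any general* as a non-event, which is the same problem again. The local row needs the local condition (7.6.2), the general row the general condition (7.6.1), and only *any* should use 7.6.3.

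**The case against.** The best defence is that a combined table cannot follow both rules of Protocol 11.6.1. Keeping all vaccinated subjects retains every observed unsolicited AE, possibly a serious one, and is a natural N for the MedDRA-coded combined analysis that 7.6.5 goes on to define. The cost is real but small: an unsolicited AE in a subject without a diary still appears in the unsolicited tables, where N stays all vaccinated. So the trade-off does not justify counting unrecorded reactions as absent.

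The plan also limits and partly discloses the problem. Protocol 6.5.10 has unreturned cards pursued by telephone or other means, and SAP 7.6 uses queries to keep missing recordings few. SAP 7.5.1 warns that N differs between tables, and SAP 7.8 tabulates screen compliance by dose and group. Table formats sit in the OPS, which is not among the documents. These points stand. They let a careful reader find the cause, but do not correct the percentage. They do rule out saying that the two tables cannot be read together at all.

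Three stronger readings are tempting and not supported:

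- **That this is the trial's overall 7-day reactogenicity result.** The secondary endpoints (Protocol 11.2, SAP 4.2) are solicited symptoms within 7 days and, separately, unsolicited AEs within 30 days. The protocol-planned 7-day summary is the solicited-only one, which uses documented subjects. The combined table is a supplementary addition in SAP 6.4.2.
- **That the bias is certain or large.** It is zero with full diary return, and no document suggests that 10% of cards will be missing. One missing card moves the figure by 1.4 points, against a CI about 20 points wide.
- **That the dose 2 row includes Revaccination subjects never given dose 2.** SAP 6.4.2 tabulates by dose given, and the natural reading of that row is subjects who received it. No section says otherwise.

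**Conclusion.** The inconsistency is explicit in the text: SAP 7.6.5 departs from the documented-only rule that Protocol 11.6.1 and SAP 5.1, 7.5.1, 7.6.1 and 7.6.3 apply to solicited symptoms. If any diary is missing, the combined Days 0-6 percentage is biased downwards, and it falls below the solicited-only figure when too few subjects qualify through an unsolicited AE alone.

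The size depends on compliance, which the documents do not forecast: nothing with full return, about 1.4 points for one missing diary in 60 and about 4 points for three. These figures assume about 85% with a solicited AE and no unsolicited-only subjects; a lower event rate or more such subjects makes the gap smaller. The 8.5 points for six missing diaries is an illustration, not an expectation. No test or success criterion is affected, and the solicited-only results stand. This is a limited flaw in one supplementary descriptive table that is cheap to correct.

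**What to change.** In SAP 7.6.5, for the Days 0-6 combined table of 6.4.2 only, set N row by row among subjects who received the dose:

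- *any local*: local symptom screen completed;
- *any general*: general symptom screen completed;
- *any*: the 7.6.3 condition.

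For the overall-per-subject columns, apply the same condition to at least one dose, as in SAP 7.5.1. Each row then matches its solicited-only counterpart. Add a combined-analysis entry to the 7.5.1 counting table so that the rule is stated once.

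At minimum, keep the all-vaccinated version, put the documented-only version beside it and show both Ns.

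Keep all vaccinated subjects as N for the unsolicited-only tables, and list any unsolicited AE in a subject without a completed screen. The cost is a short SAP edit and new denominators in one table set. The downside is that a few observed unsolicited AEs would appear only in those other tables or the listing.
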